6.3 Product Allocation and Blinding

6.3.1 Methods of Assigning Subjects to Product Arms

Randomization will be conducted through the Interactive Web and Voice Response System (IXRS).

Subjects will be randomized to 1 of the 3 arms. Each sex and each of the current CC consumption levels (10-19 CC/day and >19 CC/day) will have a quota applied to ensure they represent at least 40% of the total study population.

Four separate randomization lists were provided (male smokers who smoke 10-19 CC/day, female smokers who smoke 10-19 CC/day, male smokers who smoke >19 CC/day, and female smokers who smoke >19 CC/day). Block randomization is used within each stratum (i.e., each list) in a 2:1:1 ratio (THS 2.2:CC:SA).

The randomization scheme is generated by a statistical division within [REDACTED] and none of the study team (including study sponsor and [REDACTED] investigators and study subjects will be exposed to the live randomization codes prior to randomization.

6.3.2 Blinding

This is an open-label study; therefore, the subjects and investigators will be unblinded to subject's product assignment after randomization. However, there will be a limited degree of blinding in the data review and data analysis process. In particular, PMI and [REDACTED] personnel will be blinded to the randomized product as summarized in the following table (Table 2 "Blinding Scheme"):

**Table 2: Blinding Scheme**

Blinded Study Personnel	End of Blinding Period
PMI and [REDACTED] study statisticians	After the SAP finalization or database lock ¹ , whichever comes last.
PMI study data managers	After the finalization of PMI blind database review ¹ .
PMI safety and clinical scientist	After the finalization of PMI blind database review ¹ . Can be actively un-blinded before that time point in case of the occurrence of any safety question, when appropriate.

¹ As part of the PMI Quality Control (QC) activity, data listings will be reviewed by [REDACTED] and PMI before database lock, with no access to the randomization information. Full details will be available in the data review plan.

Any PMI and [REDACTED] personnel who are not listed in the above table will be unblinded by default.

Data will not be made available from the unblinded study team to blinded study team without a dummy randomization or masking in place, and any communications among the two groups will avoid the use of subject randomization information until database lock. PMI will receive blinded data for the pre-analysis data review as planned in the data review plan.

6.3.3 Compliance to Product Allocation

Compliance for all arms will be ensured by strict distribution of the products (product by product) and collection of used THS Tobacco Sticks and the CC butts after use will be documented in appropriate logs.

In addition, in subjects in the SA arm, the compliance will be chemically verified using exhaled CO breath. The cut-off point for the CO breath test value to distinguish subjects in the SA arm with CC use vs. no CC use will be 10 ppm (Bennowitz et al. 2002). No subjects from the SA arm will be withdrawn from the study if their exhaled CO breath test results are >10 ppm.

7 DERIVED AND COMPUTED VARIABLES

Mean change from baseline (baseline is defined in Section 12.1.4 “Definitions for Statistical Data Analysis”) is the mean of all individual subjects’ change from baseline values. Each individual change from baseline will be calculated by subtracting the individual subject’s baseline value from the value at the timepoint. The individual subject’s change from baseline values will be used to calculate the mean change from baseline.

Mean percent change from baseline is the mean of all individual subjects’ percent change from baseline values. Each percent change from baseline will be calculated by subtracting

the individual subject's baseline value from the value at the desired timepoint and then dividing this calculated value by the individual subject's baseline value and multiplying by 100. These individual subjects' percent changes from baseline values will be used to calculate the mean percent change from baseline.

When the baseline value is 0, 1 will be used in the denominator for calculating the percent change from baseline.

The QT interval corrected using Bazett's formula (QTcB) will be calculated as follows:

$$QTcB = \frac{QT}{\sqrt[2]{\frac{60}{HR}}}$$

The QT interval corrected using Fridericia's formula (QTcF) will be calculated as follows:

$$QTcF = \frac{QT}{\sqrt[3]{\frac{60}{HR}}}$$

Reported BMI will be calculated at site from the body weight and height using the following formula:

$$BMI = \frac{\text{weight in kilograms}}{\text{height in meters}^2} \quad (\text{kg/m}^2)$$

7.1 Biomarkers

Values below the Lower Limit of Quantification (LLOQ) for BoExp and risk markers will be imputed using LLOQ/2. For values above the Upper Limit of Quantification (ULOQ) i.e., preceded by a ">", for example ">xx", the numerical xx will be used for calculation and reporting in summary tables. The number of values below LLOQ or above ULOQ will be presented in each summary table.

7.1.1 Biomarkers of Exposure

The adjustment of the urinary BoExp concentration for creatinine will be calculated as:

$$\text{Biomarker (corrected for creatinine)} = \frac{[\text{Biomarker}]}{[\text{Creatinine}]}$$

where the [] indicated concentrations measured from the same 24 hour urine collection.

The quantity excreted for a BoExp over 24 hours will be calculated as:

$$\text{Quantity Excreted over 24 hours} = [\text{Biomarker}] * \text{urine volume}$$

where the concentration and the urine volume are from the same 24 hour urine collection.

7.1.2 Risk Markers

For those risk markers measured in urine an adjustment of the concentration for creatinine in urine will be calculated as:

$$\text{Risk Marker (corrected for creatinine)} = \frac{[\text{Risk Marker}]}{[\text{Creatinine}]}$$

where the concentrations are measured from the same 24 hour urine collection.

The quantity excreted for the risk markers measured in urine over 24 hours will be calculated as:

$$\text{Quantity Excreted over 24 hours} = [\text{Risk Marker}] * \text{urine volume}$$

where the concentration and the urine volume are from the same 24 hour urine collection.

7.1.3 Nicotine Equivalents

The quantity excreted of NEQ over 24 hours will be derived according to the formula below. The concentrations reported for free nicotine and its five major metabolites will not be used as analysis variables.

$$\begin{aligned} \text{NEQ [g]} &= (\text{free nicotine}_c [\mu\text{mol/L}] + \text{nicotine-glucuronide}_c [\mu\text{mol/L}] \\ &\quad + \text{free cotinine}_c [\mu\text{mol/L}] + \text{cotinine-glucuronide}_c [\mu\text{mol/L}] \\ &\quad + \text{free } \textit{trans}-3'-\text{hydroxycotinine}_c [\mu\text{mol/L}] \\ &\quad + \textit{trans}-3'-\text{hydroxycotinine-glucuronide}_c [\mu\text{mol/L}]) \\ &\quad * 162.2 [\mu\text{g}/\mu\text{mol}] * \text{urine volume (L)} / 1000 [\mu\text{g}/\text{mg}] \end{aligned}$$

N.B. All concentrations must be in $\mu\text{mol/L}$ before applying the above formula.

The conversion factors will be applied as follows:

Free nicotine	The molecular weight is 162.232 g/mol (Chemical Information Specialized Information Services RN:54-11-5). Therefore to convert nicotine from ng/mL to ng/mol, the result in ng/mL is multiplied by 6.164.
Nicotine glucuronide	The molecular weight is 338.356 g/mol (Chemical Information Specialized Information Services RN:152306-59-7). Therefore to convert nicotine from ng/mL to ng/mol, the result in ng/mL is multiplied by 2.955.
Cotinine	The molecular weight is 176.218 g/mol (Chemical Information Specialized Information Services RN:486-56-6). Therefore to transform cotinine from ng/mL to nmol/L, the result in ng/mL will be multiplied by 5.675.
Cotinine-glucuronide	The molecular weight is 352.341 g/mol (Chemical Information Specialized Information Services RN:139427-57-9). Therefore to transform cotinine from ng/mL to nmol/L, the result in ng/mL will be multiplied by 2.838.
Trans-3'hydroxycotinine	The molecular weight is 192.217 g/mol (Chemical Information Specialized Information Services RN:34834-67-8). Therefore to transform trans-3' hydroxycotinine from ng/mL to nmol/L, the result in ng/mL is multiplied by 5.202.
Trans-3'hydroxycotinine-glucuronide	The molecular weight is 368.34 g/mol (Chemical Information Specialized Information Services RN:132929-88-5). Therefore to transform trans-3' hydroxycotinine from ng/mL to nmol/L, the result in ng/mL is multiplied by 2.715.

The adjustment of NEQ for creatinine in urine will be calculated as:

$$\text{NEQ (corrected for creatinine)} = \frac{[\text{NEQ}]}{[\text{Creatinine}]}$$

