12.6.3.6.1 Relationship Between Risk Markers, BoExp and NEQ

The relationship between risk markers and BoExp will not be reported as stated in Section 9 “Changes from the Protocol Specified Statistical Analysis”.

The relationship between risk markers, and NEQ will be examined by fitting a general linear model (glm) with terms for baseline and Day 5 NEQ for each treatment arm separately. The SAS code to be used is as shown below:

```
Proc glm data=_data_ ;
  Model Risk marker = baseline NEQ Day 5 NEQ;
  Run;
```

The slope along with 95% CIs and the p-value will be presented for each analysis.

In addition scatterplots of each risk marker separately with NEQ, with the regression from the above model shown on the plot if there was a significant slope from the above model.

In these plots the risk marker will be on the y-axis.

The data will be presented in the below outputs, the TFL number refers to the TFL number in the accompanying TFL shell document:

TFL number	Title
FIGURES	
15.1.2.40	Scatterplot of 8-epi-PGF2 α Urinary Concentration Adjusted for Creatinine vs. NEQ Urinary Concentration Adjusted for Creatinine – FAS
15.1.2.41	Scatterplot of Urinary 8-epi-PGF2 α Quantity Excreted over 24 hours vs. Urinary NEQ Quantity Excreted over 24 hours – FAS
15.1.2.42	Scatterplot of 11-DTX-B2 Urinary Concentration Adjusted for Creatinine vs. NEQ Urinary Concentration Adjusted for Creatinine – FAS
15.1.2.43	Scatterplot of Urinary 11-DTX-B2 Quantity Excreted over 24 hours vs. Urinary NEQ Quantity Excreted over 24 hours – FAS
TABLES	
15.2.4.58	Statistical Analysis of the Relationship Between Risk Markers and NEQ – FAS

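### SAP 7.1.3 is inconsistent in its units for nicotine equivalents: a milligram formula labelled in grams, nmol/L factors where µmol/L is required, and an NEQ concentration that is only implied

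*SAP*

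**What the plan says.** SAP 7.1.3 opens with the derived quantity: "The quantity excreted of NEQ over 24 hours will be derived according to the formula below". The formula is headed NEQ [g]. It adds six concentrations, each marked µmol/L (free and glucuronidated nicotine, cotinine and trans-3'-hydroxycotinine), then multiplies by 162.2 µg/µmol and by urine volume in litres, and divides by 1000 µg/mg. A note follows: "N.B. All concentrations must be in $\mu\text{mol/L}$ before applying the above formula".

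A table then gives the conversion factors to apply. For free nicotine: "Therefore to convert nicotine from ng/mL to ng/mol, the result in ng/mL is multiplied by 6.164". For nicotine glucuronide: "Therefore to convert nicotine from ng/mL to ng/mol, the result in ng/mL is multiplied by 2.955". The other four rows name nmol/L as the target, for example "Therefore to transform cotinine from ng/mL to nmol/L, the result in ng/mL will be multiplied by 5.675".

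The section ends with the creatinine adjustment, [NEQ]/[Creatinine], and does not define [NEQ]. SAP 7.1.1 explains that square brackets denote concentrations from the same 24-hour collection, and that quantity excreted is concentration times urine volume.

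NEQ is used in two main places. SAP 5.2 lists it, as quantity and as creatinine-adjusted concentration, under the objective on Day 5 nicotine levels, and 12.6.2.1 analyses it with the log-transformed urinary biomarkers. SAP 12.6.3.6.1 regresses each risk marker on baseline and Day 5 NEQ: "The slope along with 95% CIs and the p-value will be presented for each analysis". SAP section 9 assigns that regression to the clinical study report.

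**The concern.** A derivation rule should lead two independent programmers to the same number in the same unit. Here the heading, the unit chain, the note and the conversion table do not agree, and one formula is left to inference. Each gap can be closed correctly by a careful reader, but the section does not close it.

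Absolute quantities are at stake: the tabulated NEQ levels by arm and day, and the risk-marker slopes per unit of NEQ. CYP1A2 and CYP2A6 (7.1.4 and 7.1.5) also use ng/mL-to-nmol/L factors, but those endpoints are ratios of two converted values, so a common power of ten cancels. In NEQ the converted values are summed and carried into a mass, so it does not cancel.

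**Working it through.** **Step 1: unit of the result.** From the printed formula: µmol/L × µg/µmol × L = µg, and µg ÷ (1000 µg/mg) = mg. The heading says g, so the label is off by a factor of 1000.

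**Step 2: reproduce the six factors.** Molecular weights (MW) are those printed in 7.1.3. Since 1 ng/mL = 1 µg/L, dividing by MW in g/mol gives µmol/L, and multiplying by 1000/MW gives nmol/L.

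| Analyte | MW | 1000/MW | Printed factor | Printed target |
|---|---|---|---|---|
| Free nicotine | 162.232 | 6.1640 | 6.164 | ng/mol |
| Nicotine glucuronide | 338.356 | 2.9555 | 2.955 | ng/mol |
| Cotinine | 176.218 | 5.6748 | 5.675 | nmol/L |
| Cotinine glucuronide | 352.341 | 2.8382 | 2.838 | nmol/L |
| Trans-3'-hydroxycotinine | 192.217 | 5.2025 | 5.202 | nmol/L |
| Trans-3'-hydroxycotinine glucuronide | 368.34 | 2.7149 | 2.715 | nmol/L |

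All six printed numbers are correct to three decimals as ng/mL-to-nmol/L factors. For µmol/L they would be 1000 times smaller.

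**Step 3: run the formula on illustrative data.** Assumed, not from the documents: 1000 ng/mL of each analyte, 1.5 L of urine, creatinine 1 g/L. The factors sum to 25.549, so the total is 25,549 nmol/L = 25.549 µmol/L.

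- (a) Note obeyed: 25.549 × 162.2 × 1.5 / 1000 = 6.216. Computing from 1/MW directly also gives 6.216 mg. The number is right in mg; read as g it is 1000-fold too high (the true value is 0.006216 g).
- (b) Listed factors entered directly: 25,549 × 162.2 × 1.5 / 1000 = 6216. This is 1000-fold too high as mg and 1,000,000-fold too high as g.
- (c) Only the four nmol/L rows divided by 1000, the two ng/mol rows left as they stand: (9119 + 16.430) × 162.2 × 1.5 / 1000 = 2222.7, about 358-fold too high for this mix. This is one possible misreading, not an expected outcome. Its factor would vary with each subject's metabolite mix.

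**Step 4: creatinine adjustment.** The NEQ concentration is 25.549 × 162.2 / 1000 = 4.144 mg/L, so the adjusted value is 4.144 mg/g at 1 g/L creatinine. Putting the 24-hour quantity in place of [NEQ] gives 6.216. The ratio 6.216/4.144 = 1.5 is the urine volume in litres. If volumes ran from 0.8 to 3 L (assumed), the factor would run from 0.8 to 3.

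**Step 5: what a scale error does downstream.** In cases (a) and (b) every NEQ value is multiplied by the same constant.

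- On the log scale this adds a constant to every Day 5 value and every baseline value. The intercept absorbs it and the THS 2.2 to CC contrast does not move. In a simulated example with 80 and 40 subjects the geometric mean ratio was 0.8591 before and after multiplying by 1000.
- In the risk-marker regression the code shows NEQ untransformed. Multiplying NEQ by 1000 divides the slope and its confidence limits by 1000 and leaves the p-value unchanged.
- The volume error of Step 4 is not constant across subjects. It could shift an arm ratio if volumes differed between arms, and it would add noise.

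**The case against.** The strongest reply is that the section, read with care, gives the right answer. Each term of the formula is marked µmol/L, the note repeats the requirement, and the divisor is printed in µg/mg, so mg is plainly intended. A programmer who follows these gets the correct figure, and only the heading is wrong. The bracket convention in 7.1.1 makes [NEQ] the same formula without the volume term. The six factors are numerically correct. Table units belong to a separate shell document, and loss of a single letter from the label cannot be excluded.

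Much of this stands. A reader might infer that NEQ will come out wrong by 1000-fold or more. The documents do not support that, because the result requires ignoring the µmol/L note or the printed divisor. A reader might also infer that the creatinine adjustment has no concentration to divide. That too is unsupported, because 7.1.1 supplies the meaning of the brackets; and misuse of the quantity would err by the volume in litres, not by 1000.

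It does not remove the point. The conversion table is an instruction, and it ends in a different unit from the one the note demands. Two rows name a unit that is not a concentration. For other biomarkers [Biomarker] is a measured concentration, whereas NEQ is a derived sum whose concentration formula appears nowhere. A lost letter would explain only the heading.

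**Conclusion.** SAP 7.1.3 contradicts itself on units and should be corrected. The result label is wrong by a factor of 1000. The six factors yield nmol/L where µmol/L is required, with the division by 1000 unwritten and two targets misnamed. The NEQ concentration is implied rather than stated.

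The effect depends on how the section is programmed. If the note and divisor are followed, the value is correct in mg and mislabelled. If the factors are entered directly, absolute levels are 1000-fold too high in mg (a million-fold if read as g), and risk-marker slopes are too small by the same factor. These multiples follow from the printed units and do not depend on the illustrative data.

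Constant scale errors leave the log-scale THS 2.2 versus CC ratio and the p-values unchanged. The four primary endpoints do not use NEQ, so the success criterion is not touched. This is a correction to a secondary endpoint's derivation, worth making because it is definite and cheap.

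**What to change.** In SAP 7.1.3:

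1. Label the result NEQ [mg/24 h].
2. Change ng/mol to nmol/L in the two nicotine rows and add an explicit division by 1000 to reach µmol/L. Alternatively, print the factors as ng/mL to µmol/L in the same row order: 0.006164, 0.002955, 0.005675, 0.002838, 0.005202, 0.002715.
3. State the concentration for the creatinine adjustment: [NEQ] (mg/L) = sum of the six µmol/L values × 162.2 / 1000, without urine volume, divided by creatinine concentration from the same 24-hour collection.
4. Check that the units in the NEQ table shells and the risk-marker slope table match.

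The cost is SAP wording and one check of the derivation program against a hand-worked subject. No new data are needed.

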7.1.4 CYP1A2

CYP1A2 activity is calculated as the molar metabolic ratio of PX / CAF in plasma, both expressed in molar equivalent (nmol/L).

The conversion factor will be applied as follows:

PX	The molecular weight is 180.166 g/mol (Chemical Information Specialized Information Services RN:611-59-6). Therefore to convert PX in ng/mL to nmol/L the result in ng/mL is multiplied by 5.550.
CAF	The molecular weight is 194.193 g/mol. (Chemical Information Specialized Information Services RN:58-08-2). Therefore to convert CAF in ng/mL to nmol/L the result in ng/mL is multiplied by 5.150.

The converted results will be calculated to three decimal places and the ratio will be reported as a percentage with two decimal places.

If either of the PX or CAF concentration is LLOQ then the ratio will not be calculated.

7.1.5 CYP2A6

CYP2A6 activity is calculated in plasma as the metabolic ratio of trans-3' hydroxycotinine to cotinine, both expressed in molar equivalent (nmol/L) (Jacob et al. 2011).

The conversion factor will be applied as follows:

Cotinine	The molecular weight is 176.215 g/mol (Chemical Information Specialized Information Services RN:486-56-6). Therefore to transform cotinine from ng/mL to nmol/L, the result in ng/mL will be multiplied by 5.675.
Trans-3'hydroxycotinine	The molecular weight is 192.217 g/mol (Chemical Information Specialized Information Services RN:34834-67-8). Therefore to transform trans-3' hydroxycotinine from ng/mL to nmol/L, the result in ng/mL is multiplied by 5.202.

The converted results will be calculated to three decimal places and the ratio will be reported as a percentage with two decimal places.

If either of the cotinine or trans-3'hydroxycotinine concentration is LLOQ then the ratio will not be calculated.

7.1.6 Laboratory Parameters

Values below the Lower LLOQ will be handled as described in Section 7.1, "Biomarkers".

When the baseline value is 0, 1 will be used in the denominator for calculating the percent change from baseline.

7.2 Pharmacokinetic Parameters

The peak nicotine and cotinine plasma concentration (C_{peak}) and time to peak concentration (t_{peak}) will be obtained directly from the concentrations taken on Day 5. The weighted average concentration over 24 hours on Day 5 (C_{avg}) will be calculated by dividing the area under the curve from 0 to 24 h ($AUC_{0-24\text{ h}}$) by 24, where the $AUC_{0-24\text{ h}}$ is calculated using the linear trapezoidal rule.

Since the samples are taken whilst the subjects are smoking freely all samples must be non-missing for the parameters to be calculated as C_{peak} (and t_{peak}) could occur at any time.

7.3 Questionnaires

All used questionnaires, except the cough and HST questionnaires, are available as a validated questionnaire in Polish. The cough and HST questionnaires will be forward-translated and back-translated with subsequent independent verification.

7.3.1 Fagerström Test for Nicotine Dependence (FTND)

The FTND will be used in its revised version (Heatherton et al 1991), as updated in 2012 (Fagerström et al. 2012). These questions are to be answered by the subject themselves. It is conducted at Screening only to determine subject's dependence on nicotine.

Table 3 describes the six questions the questionnaire consists of, and the scores associated with each question.

The FTND total score will be derived by summing the individual item scores if all items are non-missing, otherwise the total score will be set to missing. For the FTND total score, descriptive statistics and frequency tables according to the following classification will be provided (Fagerström et al. 2012):

Mild	0 – 3
Moderate	4 – 6
Severe	7 – 10

Table 3: Scoring for the Fagerstrom Test for Nicotine Dependence

	FTND Question	Response	Score
1	How soon after you wake up do you smoke your first cigarette?	
▪ Within 5 minutes▪ 6 to 30 minutes▪ 31 to 60 minutes▪ After 60 minutes	
3210
2	Do you find it difficult to refrain from smoking in places where it is forbidden?	
▪ Yes▪ No	
10
3	Which cigarette would you hate most to give up?	
▪ The first one in the morning▪ Any other	
10
4	How many cigarettes per day do you typically smoke?	
▪ 10 or less (up to ½ pack)▪ 11 to 20 (a little more than ½ pack, up to a full pack)▪ 21 to 30 (a little more than a pack, up to 1½ packs)▪ 31 or more (more than 1½ packs)	
0123

**Table 3: Scoring for the Fagerstrom Test for Nicotine Dependence**

	FTND Question	Response	Score
5	Do you smoke more frequently during the first hours after waking than during the rest of the day?	
 Yes No	
10
6	Do you smoke if you are so ill that you are in bed most of the day?	
 Yes No	
10

If the baseline score is 0, the percent change from baseline will be calculated using a value of 1 for the denominator.

7.3.2 Questionnaire of Smoking Urges-Brief (QSU-brief)

The QSU-brief (Cox et al. 2001) is a self-reported questionnaire completed daily from Day -1 to Day 5 between 08:00 PM and 11:00 PM.

The QSU-brief consists of 10 items as presented in Table 4.

Table 4: Questionnaire of Smoking Urges Brief - Questions and Factors

	Question	Factor
1	I have a desire for a cigarette right now	1
2	Nothing would be better than smoking a cigarette right now	2
3	If it were possible, I probably would smoke now	1
4	I could control things better right now if I could smoke	2
5	All I want right now is a cigarette	2
6	I have an urge for a cigarette	1
7	A cigarette would taste good now	1
8	I would do almost anything for a cigarette now	2
9	Smoking would make me less depressed	2
10	I am going to smoke as soon as possible	1

All items will be rated on a 7-point scale, ranging from 1 (strongly disagree) to 7 (strongly agree). Higher scores indicate a higher urge to smoke.

Two factor scores and a total score will also be derived (Cox et al. 2001). Each factor is a subset that includes 5 of the 10 questions as defined in Table 4 “Questionnaire of Smoking Urges Brief - Questions and Factors”. Factor 1 represents the desire and intention to smoke with smoking perceived as rewarding, while Factor 2 represents an anticipation of relief from negative effect with an urgent desire to smoke.

The factors and total scores will be calculated by averaging non-missing item scores if at least 50% are non-missing, otherwise the factor or total score will be set to missing.

